5.7 Duration of Follow-up

All patients will be followed as according to the protocol calendar in Section 7.0 for the duration unless the patient withdraws consent or is lost-to-follow-up. Following the safety follow-up visit, patients will continued to be monitored for survival and late-onset toxicity every 3 months for up to 6 months. For these long-term follow-up visits, a telephone visit can be made in lieu of a physical visit.

5.8 Lost to Follow-Up

A participant will be considered lost to follow-up if he or she fails to return for 3 scheduled visits and is unable to be contacted by the study team.

The following actions must be taken if the participant fails to return to clinic for a required study visit:

- The study team will attempt to contact the participant and reschedule the missed visit within 1 week and counsel the participant on the importance of maintaining the assigned visit schedule and ascertain if the participant wishes to and/or should continue in the study.
- Before a participant is deemed lost to follow-up, the investigator or designee will make every effort to regain contact with the participant (where possible, 3 telephone calls and, if necessary, a certified letter to the participant's last known mailing address). These contact attempts should be documented in the participant's medical record or study file.
- Should the participant continue to be unreachable, he or she will be considered to have withdrawn from the study with a primary reason of lost to follow-up.

6.0 PHARMACEUTICAL INFORMATION

6.1 Duvelisib

6.1.1 Description

Duvelisib is a dual inhibitor of phosphatidylinositol 3-kinases PI3K- δ and PI3K- γ . Duvelisib is a white-to-off-white crystalline solid with the empirical formula $C_{22}H_{17}ClN_6O \cdot H_2O$ and a molecular weight of 434.88 g/mol. Hydration can vary with relative humidity. Duvelisib contains a single chiral center as (S) enantiomer. Duvelisib is soluble in ethanol and practically insoluble in water. Duvelisib is

described chemically as a hydrate of (S)-3-(1-(9H-purin-6-ylamino)ethyl)-8-chloro-2-phenylisoquinolin-1(2H)-one.

6.1.2 Dose Forms and Strengths

Duvelisib capsules are for oral administration and are supplied as white to off-white opaque and Swedish orange opaque capsules (25 mg, on anhydrous basis) or pink opaque capsules (15 mg, on anhydrous basis), and contain the following inactive ingredients: colloidal silicon dioxide, crospovidone, magnesium stearate, and microcrystalline cellulose. Capsule shells contain gelatin, titanium dioxide, black ink, and red iron oxide.

Placebos are supplied as matching size white to off-white opaque capsules containing the inactive above.

6.1.3 Storage and Stability

Store at room temperature 20°C to 25°C (68°F to 77°F); excursions are permitted between 15°C and 30°C (59°F and 86°F).

6.1.4 Availability

Duvelisib is commercially available by prescription. For this study, duvelisib or placebo will be supplied without charge to the participants by Verastem Oncology, the maker of duvelisib.

6.1.5 Preparation

Not applicable for capsule administration. For nasogastric/orogastric tube administration see Section 5.1.

6.1.6 Administration

Please see Section 5.1.

6.1.7 Warnings and Precautions

Fatal and/or serious diarrhea or colitis occurred in 18% of duvelisib-treated patients. Monitor for the development of severe diarrhea or colitis.

Fatal and/or serious cutaneous reactions occurred in 5% of duvelisib-treated patients.

Fatal and/or serious pneumonitis occurred in 5% of duvelisib-treated patients. Monitor for new/evolving pulmonary symptoms and interstitial infiltrates.

7.0 SCHEDULE OF ASSESSMENTS

	Screening ¹	Study Treatment Days											Safety Follow-Up ¹¹	
		-1	1	2	3	4	5	6	7	8	9	10	15	29
Informed Consent	X													
Medical History	X													
Physical Exam w/ vital signs and O2 saturation ²	X	X	X	X	X	X	X	X	X	X	X	X	X	X
APACHE II Score		X										X		
SOFA Score		X										X		
CBC ²	X	X	X	X	X	X	X	X	X	X	X	X	X	X
CMP ²	X	X	X	X	X	X	X	X	X	X	X	X	X	X
Ferritin ²	X	X	X	X	X	X	X	X	X	X	X	X	X	X
D-Dimer ¹⁰	X		X	X		X				X			X	X
aPTT and PT/INR ¹⁰	X		X	X		X				X			X	X
Fibrinogen ¹⁰	X		X	X		X				X			X	X
C-reactive peptide ²	X	X	X	X	X	X	X	X	X	X	X	X	X	X
SARS-CoV-2 viral load ³	X	X	X	X	X	X	X	X	X	X	X	X	X	X
Quantitative immunoglobulins (IgA, IgG, IgM)	X													
Immune competence assessment	X													X
CMV IgG	X													
CMV DNA PCR (CMV seropositive pts)	X									X ⁸				
Serum βhCG ⁴	X													
Chest X-ray ⁵	X													
Electrocardiogram ⁵	X													
ECHO or MUGA ⁵	X													
Plasma troponin and NT-proBNP ⁵	X													
Duvelisib/placebo ⁶			X	X	X	X	X	X	X	X	X	X		
PJP prophylaxis ⁷			X	X	X	X	X	X	X	X	X	X	X	X

Correlative studies ⁹	X ¹²			X		X				X		X	X	X
Adverse event monitoring			Continuously											

- 1 – Within 7 days of registration
- 2 – Performed daily while inpatient or per local SOC. If outpatient, visits may occur within +/- 2 days from schedule
- 3 – Performed daily through Day +10 then weekly thereafter by NP or OP
- 4 – Women of childbearing potential only
- 5 – Not required at Screening if patient meets Inclusion Criterion 1 by other measures. Repeated on study if clinically indicated.
- 6 – Duvelisib or placebo will be administered twice daily for up to 10 days. See section 5.0 for treatment administration details.
- 7 - Continued until CD4+ T cells >200 cells/μL. Choice of agent per institutional guidelines and patient tolerance.
- 8 – CMV viral load monitoring should occur at screening, and on D8 in patients who are CMV seropositive (positive IgG at screening). CMV prevention/treatment should follow institutional guidelines.
- 9 – Collected on the first 10 patients enrolled onto study. A variance of +/- 2 days for correlative collection will be permitted.
- 10 – Performed as scheduled or more frequently if clinically indicated for coagulopathy monitoring
- 11 – Outpatient follow-up visits may be performed by telemedicine/telephone encounter without lab assessment in situations that preclude in-person visits (eg. discharge to skilled nursing facility, lack of transportation, persistent COVID precautions)
- 12 – May occur anytime from screening through Day 1 pre-dose.

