5.0 STUDY TREATMENT

5.1 Overview

Patients will be randomly assigned in a double-blind fashion to receive either duvelisib 25mg or placebo twice daily for up to 10 days. Patients who have significant clinical improvement prior to day 10 and are going to be discharged from the hospital may discontinue the treatment early with investigator permission.

Blocks of 10 patients will be used to allocate patients to duvelisib or placebo. Due to differences in color between the duvelisib and placebo capsules, we will employ methods in this trial to maintain the blinding of the investigator to the best of our ability (e.g. having the drug dispensed by alternative personnel). If this study were to lead to a pivotal trial, matched placebos would be manufactured for such a trial.

Treatment is dosed orally and can be administered with or without food. For patients unable to administer orally, a duvelisib suspension will be administered through a nasogastric/orogastric tube. In this event, the capsule(s) will be opened and the dose will be placed in 40mL water and stirred until dissolved. The suspension should be administered using an appropriate syringe within 6 hours after preparation. Following administration, the tube should be rinsed with approximately 75 mL of water.

If a dose is missed by fewer than 6 hours, administer the missed dose right away and take the next dose as usual. If a dose is missed by more than 6 hours, the patient should not take an additional dose, but should take the next usual prescribed dose.

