10.0 REGULATORY AND REPORTING REQUIREMENTS

The entities providing oversight of safety and compliance with the protocol require reporting as outlined below. Please refer to Appendix C for definitions and Appendix D for a grid of reporting timelines.

Adverse events will be tracked from start of treatment through Day 29. All adverse events must be recorded on the toxicity tracking case report form (CRF) with the exception of:

- Baseline adverse events, which shall be recorded on the medical history CRF

Refer to the data submission schedule in Section 9 for instructions on the collection of AEs in the EDC.

Reporting requirements for Washington University study team may be found in Section 10.1. Reporting requirements for secondary site study teams participating in Washington University-coordinated research may be found in Section 10.2.

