12.2 Statistical Analysis Plan

The primary endpoint is 28 day overall survival (OS) and will be treated as a binary outcome for the purposes of the primary analysis and will be described using descriptive statistics with the corresponding 95% confidence intervals. This will be an intent-to-treat analysis, and all patients randomized will be included in the analysis. The assumption is that all patients will be followed for at least 28 days. Patients who are lost to follow-up for any reason prior to this point will be included in the analysis and considered treatment failures and treated the same as a death. The 28 day OS of each cohort, duvelisib versus placebo, will be compared using Fisher's exact test of independence.

In addition to the primary analysis, OS will be treated as a time-to-event variable and will be described using Kaplan-Meier product limit estimators of event time curves and, if reached, medians with 95% confidence intervals. Cox proportional hazards models may be used to adjust for potential confounding effects. These analyses are considered exploratory, and we acknowledge that the proposed sample size will have low power for such adjustment.

The analyses of secondary end points are all exploratory in nature. Secondary endpoints of efficacy include: hospital and ICU length of stay and duration of ventilator (for those on a ventilator at the time of randomization), vasopressors, and renal replacement therapy. Kaplan-Meier product limit estimators of event time curves and, if reached, medians with 95% confidence intervals, and compared between cohorts using the Log-Rank test. For these analyses, patients will be censored at Day 28 or at death, whichever is earlier. Secondary end points of toxicity are viral kinetics and adverse events. The rate of viral load elevation and other adverse events of interested will be summarized using descriptive statistics and compared using Fisher's Exact tests.

Demographic and clinical characteristics of the sample and of each cohort will be summarized using descriptive statistics. For continuous variables, the number of patients, mean, standard deviation, median, minimum, maximum, and quartiles will be provided. For categorical variables, the number and percent of patients in each demographic/characteristic category will be summarized with 95% confidence intervals.

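### After Day 10 the chance of detecting a laboratory adverse event depends on whether the patient is still in hospital, and the between-arm comparison does not allow for this

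*Combined protocol and SAP*

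**What the plan says.** The grid in section 7.0 marks CBC and CMP for all patients on each of Days 1-10, then on Days 15 and 29. Footnote 2 qualifies both rows: "Performed daily while inpatient or per local SOC. If outpatient, visits may occur within +/- 2 days from schedule". Footnote 11 adds: "Outpatient follow-up visits may be performed by telemedicine/telephone encounter without lab assessment in situations that preclude in-person visits". The text does not say clearly whether a patient discharged before Day 10 still has the remaining Day 1-10 draws.

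On the counting window, section 10.0 says: "Adverse events will be tracked from start of treatment through Day 29". On the analysis, section 12.2 says that "other adverse events of interested will be summarized using descriptive statistics and compared using Fisher's Exact tests". Nothing in 12.2 refers to the number of draws or to days at risk, or limits laboratory events to common time points.

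Two passages tie discharge to treatment. Section 5.1 states: "Patients who have significant clinical improvement prior to day 10 and are going to be discharged from the hospital may discontinue the treatment early". Section 12.2 makes discharge time an outcome: "Secondary endpoints of efficacy include: hospital and ICU length of stay".

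**The concern.** A transient neutropenia, thrombocytopenia or transaminase rise is recorded only if blood is drawn while it lasts. Over Days 11-29, 19 days in all, an inpatient may be drawn daily, while an outpatient is drawn twice or not at all. If the arms differ in length of stay, they differ in the chance of detecting the same event, and a crude yes/no rate mixes toxicity with opportunity to detect it.

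Laboratory toxicity matters in this plan. Neutropenia, thrombocytopenia and Grade 4 laboratory abnormalities each have their own rule in section 5.2, and safety and tolerability is the only secondary objective. Section 12.0 says the trial is meant to generate hypotheses on toxicity as well as efficacy, so the estimated rates are what a later trial would inherit.

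**Working it through.** The plan states no figure on this point. The draw days below come from the section 7.0 grid. Discharge times, event durations and incidence are assumptions, because the documents give none.

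**Step 1. Scheduled draw days in Days 1-29.** Count Days 1 to the discharge day, plus the later outpatient draws, taking inpatient draws as daily.

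| Last inpatient day | Day 1-10 marks apply after discharge | Only Days 15 and 29 after discharge | Outpatient labs all waived |
|---|---|---|---|
| 7 | 12 | 9 | 7 |
| 10 | 12 | 12 | 10 |
| 14 | 16 | 16 | 14 |
| 20 | 21 | 21 | 20 |
| 29 | 29 | 29 | 29 |

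The two readings of footnote 2 differ only for discharge before Day 10. The gap after Day 10 exists on both.

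**Step 2. Detection by hand.** Let an abnormality last 3 days, with onset equally likely on each of Days 1-29.
- Discharge Day 10, labs kept: detected onsets are Days 1-10, 13-15 and 27-29, so 16/29 = 55%.
- Discharge Day 20, labs kept: Days 1-20 and 27-29, so 23/29 = 79%.
- Labs waived: 10/29 = 34% and 20/29 = 69%.

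With an assumed true incidence of 50% in both arms, the recorded rates are 28% versus 40% (labs kept) and 17% versus 34% (waived). For a 5-day abnormality with labs kept, detection is 20/29 versus 25/29, giving 34% versus 43%, a gap of about 9 points.

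**Step 3. Spread-out discharge times, no deaths.** Assumed: onset hazard 0.02 per day in both arms, so true risk by Day 29 is 1 − exp(−0.02 × 29) = 44%; log-normal discharge with median Day 8 versus Day 18 and log-SD 0.5. Simulated recorded rates, earlier- versus later-discharged arm:

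| Outpatient draws | 3-day event | 5-day event |
|---|---|---|
| Days 15 and 29 only | 24% vs 35% (gap about 11) | 28% vs 37% (about 9) |
| Day 1-10 marks also kept | 28% vs 35% (about 7) | 32% vs 37% (about 5) |
| Outpatient Day 15/29 labs waived | gap about 10 to 15 | gap about 10 to 15 |

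**Step 4. Add deaths.** Section 12.1 plans on 28-day survival of 20% versus 60%. Give the arm discharged sooner 60% survival, with death days assumed uniform on Days 3-28 and dying patients inpatient until death. With outpatient draws kept, the 3-day gap falls to about 3 points (Days 15 and 29 only) or 1 point (Day 1-10 marks kept). The 5-day gap falls to about 1 point, or reverses by about 2. With medians of Day 12 versus Day 18 the sign reverses in all four cases, in one of them barely.

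A simple count shows why. With deaths at Day 10, an arm with 60% survival and discharge at Day 14 averages 0.6 × 16 + 0.4 × 10 = 13.6 draw days. An arm with 20% survival and discharge at Day 20 averages 0.2 × 21 + 0.8 × 10 = 12.2.

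**Step 5. Candidate remedies, in the Step 3 setting.**
- Counting only Days 1-10, 15 and 29 leaves a gap of 0 points if those draws are made for everyone. About 3 to 4 points remain if Day 1-10 draws stop at discharge, and about 3 to 9 if outpatient labs are waived.
- A rate per sampled day overcorrects. At equal true risk it gives 0.0217 versus 0.0176 for 3-day events (ratio 1.23) and 0.0259 versus 0.0186 for 5-day events (ratio 1.39), so the arm discharged sooner looks falsely worse.
- Restriction to grid days does not correct for death. With deaths at Day 10, mean grid days are 0.6 × 12 + 0.4 × 10 = 11.2 versus 0.2 × 12 + 0.8 × 10 = 10.4.

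**The case against.** The grid marks Days 1-10 for everyone, and footnote 2 gives outpatients a window around the schedule, which suggests that the schedule still binds them. The allowance for local standard of care also means that daily inpatient draws are not guaranteed. Both points stand: a difference in scheduled sampling is certain only for Days 11-29, and a reader who infers that CBC and CMP are daily only for inpatients from Day 1 goes beyond the text.

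A reader might also infer that the arm discharged sooner must look less toxic, so that the safety result is biased in the same direction as the efficacy result. The documents do not support this. It needs a real difference in stay, and early death removes draw days from the arm with worse survival. Step 4 shows the pattern shrinking or reversing at the plan's own survival rates.

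The illustration is also generous. The 10-day difference in median stay has no source in the documents. The constant hazard puts 59% of the simulated onsets after Day 10, when dosing has ended. Some of any observed difference could be real, since patients who go home may stop treatment early and those who remain are sicker.

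The stakes are limited. Section 12.2 calls all secondary analyses exploratory and does not list which adverse events are of interest. Clinical events are monitored continuously, and viral load has its own schedule (footnote 3) that does not depend on inpatient status. At 14 per arm, 5 to 11 points is 0.7 to 1.5 patients, and a two-sided Fisher test at 0.05 would flag gaps of the size in Step 2 only 3% to 10% of the time. All this lowers the weight of the point. It does not remove the unequal opportunity to detect events, and death adds a second uncorrected distortion.

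**Conclusion.** The concern holds in a limited form. From Day 11 to Day 29, detection of transient CBC- or CMP-defined events depends on discharge, and the crude comparison in 12.2 does not allow for it. Other things equal, the arm discharged sooner shows fewer such events: about 5 to 11 points for 3- to 5-day events with outpatient labs kept, and about 10 to 15 if they are waived. These sizes assume median discharge on Day 8 versus Day 18, equal true risk and no deaths; the gap is zero if stay and survival are equal. Mortality can offset or reverse it, so neither a fixed direction nor alignment with the efficacy result can be claimed for this trial. The distortion lies in the estimates; a false significant result is unlikely. For an exploratory comparison this is a modest point, but it is cheap to put right.

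**What to change.** In 12.2, for CBC- and CMP-defined events, add a between-arm comparison restricted to the common grid days (1-10, 15 and 29). Show it beside the all-draw rate and base the between-arm interpretation of laboratory toxicity on it. Tabulate by arm the number of sampled days, the missed or waived Day 15 and Day 29 labs, and the deaths, because the restriction corrects for neither waived labs nor death. Do not use a rate per sampled day (Step 5).

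In footnote 2, state whether the Day 1-10 marks apply after discharge. Keep every event from any draw in the listings and in safety reporting.

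The cost is SAP wording, one footnote clarification and one table; the analysis change itself needs no new samples. The downside is that events found only on extra inpatient draws do not count in the restricted comparison.

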8.0 CORRELATIVE STUDIES

Correlative studies will be collected and analyzed for the first 10 patients enrolled onto the trial.

8.1 Sample Collection

Peripheral blood (20 ml) will be collected into EDTA (pink or lavender top) vacutainer tubes and 10 mL will be collected into serum (red top) vacutainer tubes at the following time points (a variance of +/- 2 days will be permitted for correlative collections):

- Screening (May occur anytime from screening through Day 1 pre-dose)
- Day 2
- Day 4
- Day 8
- Day 10
- Day 15
- Day 29

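### The uniform +/- 2 day variance does not ensure that the Day 2 correlative sample follows the first dose or that the Day 10 sample is on treatment, and it lets Days 2/4 and 8/10 overlap

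*Combined protocol and SAP*

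**What the plan says.** Section 8.1 lists a baseline sample and samples on Days 2, 4, 8, 10, 15 and 29 under a single allowance: "a variance of +/- 2 days will be permitted for correlative collections". Footnote 9 to the schedule in Section 7.0 has the same rule and limits the work to ten patients: "Collected on the first 10 patients enrolled onto study. A variance of +/- 2 days for correlative collection will be permitted".

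Only the baseline sample has a condition relating it to dosing. Footnote 12 says of it: "May occur anytime from screening through Day 1 pre-dose". No later sample must follow a dose or precede the end of treatment, and no order or minimum gap between samples is set.

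Under Section 5.1, patients "receive either duvelisib 25mg or placebo twice daily for up to 10 days", and the schedule starts dosing on Day 1. Patients who improve and are about to be discharged "may discontinue the treatment early with investigator permission".

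Section 8.3.1 uses the samples to measure the effect of treatment on antibody classes, neutralising activity, memory B cells and plasma cells. It names Days 2, 4, 8, 15 and 29, but not Day 10. Section 8.3.2 adds cytokines and other markers without giving time points. Section 12.2 contains no analysis of the correlative data.

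**The concern.** Two days of tolerance is small next to Day 29 but as large as the nominal value at Day 2. Applied uniformly, it reaches back past the first dose at one end of treatment and forward past the last dose at the other. It also equals the whole gap between Days 2 and 4 and between Days 8 and 10.

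At stake is the meaning of the sample label. A Day 2 value may contain no drug effect and may come from the same days as the baseline sample. A Day 10 value may be a post-treatment value. Two nominally different time points may represent the same day. A comparison of arms at nominal Day 2 would then mix exposed and unexposed samples, and nothing elsewhere in the plan calls for analysis by actual time. Cytokine suppression is the mechanism on which Sections 1.4 and 1.5 rest the trial, so the early samples are worth protecting.

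**Working it through.** The plan states no figure to reproduce. The check compares each permitted window with the dosing period and with its neighbours.

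**Inputs**
- Nominal days 2, 4, 8, 10, 15 and 29, each +/- 2 days (Section 8.1; Section 7.0, footnote 9).
- Dosing from Day 1 to Day 10 at most (Section 5.1; Section 7.0, footnote 6).
- Baseline sample from screening to Day 1 before the dose (Section 8.1; Section 7.0, footnote 12).
- No Day 0: Section 5.4 treats the screening day, Day -1 and Day 1 as consecutive, and the schedule goes from -1 to 1.
- Ten patients sampled (Section 8.0); allocation in blocks of 10 (Section 5.1).

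**Windows.** Permitted days are the nominal day minus 2 to plus 2. Time since the first-dose day is the day of draw minus 1. A full course to Day 10 is assumed.

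| Nominal day | Permitted days | Days since first-dose day (intended) | Permitted days not on drug |
|---|---|---|---|
| 2 | -1, 1, 2, 3, 4 | none to 3 (1) | Day -1, and Day 1 if before the dose |
| 4 | 2 to 6 | 1 to 5 (3) | none |
| 8 | 6 to 10 | 5 to 9 (7) | none |
| 10 | 8 to 12 | 7 to 11 (9) | Days 11 and 12 |
| 15 | 13 to 17 | 12 to 16 (14) | all, by design |
| 29 | 27 to 31 | 26 to 30 (28) | all, by design |

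If a Day 0 were counted, the Day 2 window would be Days 0 to 4, and it could still precede the first dose.

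**Overlap with baseline.** Day -1 and pre-dose Day 1 are permitted for both the baseline and the Day 2 sample.

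**Overlap between neighbours**
- Days 2 and 4 share Days 2, 3 and 4.
- Days 4 and 8 share Day 6 only.
- Days 8 and 10 share Days 8, 9 and 10.
- Days 10 and 15, and Days 15 and 29, share none.

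**Share of each window on dosing days.** For Day 2, 4 of 5 permitted days, with Day 1 counting only if the draw follows the dose. For Days 4 and 8, 5 of 5. For Day 10, 3 of 5.

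**Effect of one mistimed sample.** If the ten patients fill one block with equal allocation, there are 10 / 2 = 5 per arm, and one sample is 1/5 = 20% of an arm. If one of five duvelisib samples at nominal Day 2 is pre-dose and the other four carry the full effect D, the expected difference in means is (4 x D + 1 x 0) / 5 = 0.8 D.

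**Would a uniform +/- 1 day be enough?** No. Day 2 would be Days 1 to 3, and Day 1 could still be pre-dose. Day 10 would be Days 9 to 11, and Day 11 is off drug. Days 2 and 4 would still share Day 3, and Days 8 and 10 would share Day 9.

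**The case against.** A reader might go further and infer that the planned time points do not measure on-drug effects at all, or that every pair of adjacent windows overlaps. The documents support neither. The Day 4 and Day 8 windows lie wholly on dosing days for a fully dosed patient, most permitted days for Days 2 and 10 do too, and the last two pairs of windows are separate. A permitted variance also does not show that samples will be mistimed.

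The purpose of the correlatives limits the point further. Section 8.3.1 concerns the antibody response over acute infection, includes two time points that are off drug by design, and omits Day 10. The Day 10 problem therefore bears mainly on the loosely specified work in Section 8.3.2. Because Section 12.2 plans no between-arm correlative test, no stated analysis is invalidated. The same window applies to both arms, so the documents support a claim of dilution and added noise, not of distortion in favour of one arm.

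Finally, tight windows have a price. Footnote 2 allows inpatient tests to follow local practice instead of being daily, and patients may be discharged early. A missing sample costs the same 20% of an arm, whereas a mistimed sample can still be used if its actual time is known.

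All of this stands. It reduces the size of the point and argues for keeping out-of-window samples. It does not explain why a compliant Day 2 sample may precede the first dose, and the plan has no safeguard against that.

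**Conclusion.** The point holds in limited form. The uniform variance does not guarantee a post-dose Day 2 sample or an on-treatment Day 10 sample, and it does not keep Days 2 and 4, or Days 8 and 10, distinct. Exposure at nominal Day 2 can range from none to about three days, against about one intended. Two of the five days permitted for Day 10 fall after dosing.

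The consequence is confined to exploratory correlatives in ten patients. The primary endpoint, secondary endpoints, sample size and error rates are unaffected. This is an inexpensive improvement, not a flaw in the trial's main inference.

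The conclusion assumes that the days named in Section 8.3.1, which it words as days of infection, are the study days of Section 8.1. The on-drug statements for Days 4 and 8 assume a full ten-day course; with early stopping, those samples can be off drug too. The figure of 20% assumes five patients per arm from one filled block with equal allocation, which the documents do not state for the sampled subset.

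**What to change.** Amend Section 8.1 and footnote 9 together.

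- State that the Day 2 sample must be drawn after the first dose.
- Replace the uniform variance during treatment with windows that do not overlap. For example, Days 2 and 4 at 0 to +1 (Days 2 to 3 and 4 to 5), and Days 8 and 10 at -1 to 0 (Days 7 to 8 and 9 to 10). A symmetric +/- 1 for Day 8 would give Days 7 to 9 and share Day 9 with the Day 10 window.
- Keep +/- 2 days for Days 15 and 29.
- Record the date and time of each draw and of the preceding dose.
- Keep out-of-window samples, flag any drawn off drug (including after early stopping), and analyse by actual time since first dose.

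The first and the last two items matter most and cost almost nothing. The tighter windows cost scheduling flexibility and will produce an occasional out-of-window or missed sample, especially after early discharge. While patients are in hospital, the tubes can usually be taken with routine blood tests, which footnote 2 sets as daily or according to local practice.
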